4.10. Investigator Compliance

Study centers that deviate significantly from the protocol without prior approval from the Sponsor and regulatory authorities may be discontinued from the study. The Investigator at each study center is responsible for ensuring the accuracy and completeness of all research records, the accountability of study drug, and the conduct of clinical and laboratory evaluations as outlined in the protocol.

5. STUDY TREATMENTS

5.1. Study Drug Supply and Storage

All study drugs must be stored in a safe and locked place with no access by unauthorized personnel.

5.1.1. ACY-1215

ACY-1215 will be supplied by the Sponsor as a liquid (12 mg/ml) for PO administration in 20 mL glass vials. ACY-1215 will be stored in the pharmacy at -20°C. Additional storage conditions and dose preparation instructions will be provided in detail within the Pharmacy Manual.

5.1.2. Pomalidomide and Dexamethasone

Pomalidomide will be provided at 4, 3, 2, and 1 mg for PO administration. Pomalidomide will be dispensed by pharmacists to patients for the duration of their participation in this study at no charge to them or their insurance providers, through the region-specific POMALYST REMST™ or RevAid® program. Patients will have to be registered in such a program and follow the required procedures to receive pomalidomide supply. Only enough pomalidomide for one cycle of therapy will be supplied to the patient every cycle. Pomalidomide capsules are to be stored, per the package insert [51,58].

For sites in the US and Canada, dexamethasone for PO administration will be supplied from commercially-available sources as 4 mg compressed tablets. (Dexamethasone tablets at strengths other than 4 mg may be used, as necessary.) Acetylon will supply dexamethasone to sites in the EU. Dexamethasone tablets are to be stored at room temperature between 68° to 77°F (20° to 25°C) away from light and moisture.

5.2. Study Drug Dose and Administration

All patients will receive ACY-1215 in combination with pomalidomide and dexamethasone. On ACY-1215 administration days, pomalidomide and dexamethasone are to be taken immediately after ACY-1215. If the patient is receiving ACY-1215 BID, pomalidomide and dexamethasone are to be taken immediately after the first (a.m.) dose of ACY-1215 only. Study Day 1 is defined as the first day the patient receives study drug.

5.2.1. ACY-1215

ACY-1215 will be administered orally QD or BID at least 1 hour after ingestion of food and followed by 4 ounces of water. Patients will be instructed not to ingest food or other PO medication, other than pomalidomide and dexamethasone, for at least 2 hours after each ACY-1215 dose. On study center visit days requiring PK/pharmacodynamic blood draws, ACY-1215 must be taken in the study center. On other study drug administration days that coincide with scheduled study center visits, ACY-1215 may be administered at the study center or at home. If ACY-1215 is being given BID, pomalidomide and dexamethasone are to be given with the first dose of ACY-1215. The ACY-1215 BID, doses should be taken approximately every twelve hours. A plus or minus 2 hour window is acceptable for BID dosing.

One cycle of therapy is comprised of either 21 doses every 28 days (QD), or 42 doses every 28 days (BID).

Phase 1b Segment:

Study Day 1 is defined as the first day the patient receives study drug. Patients in the Phase 1b segment of the study will receive single 160 mg QD doses of ACY-1215 for 21 consecutive days of a 28-day treatment cycle (Dose Level 1). Dose escalations will follow as outlined in Table 2. If that dose is tolerated per SRC safety review, 240 mg QD on the same days will be explored (Dose Level 2). If Dose level 2 is well tolerated, Dose Level 3 of 160 mg BID will be explored. If Dose Level 1 is not tolerated, the schedule will be modified (Dose Level -1) to 160 mg ACY-1215 QD on Days 1-5, 8-12, and 15-19. If Dose Level -1 is not tolerated, the schedule will be modified (Dose Level -2) to 160 mg ACY-1215 QD on Days 1-5, and 8-12.

Based on emerging data from ongoing studies of ACY-1215, intermediate dose levels and schedules may be added, or dose levels eliminated, and the IRB/IEC will be notified.

Investigators should consider providing prophylaxis for tumor lysis, including hydration, prior to administration of ACY-1215.

Phase 2 Segment:

Based on findings from the Phase 1 segment of the study and as recommended by the SRC, the ACY-1215 dose and schedule to be administered in the Phase 2 segment will be 160 mg PO QD on Days 1 to 21 of a 28- day cycle as recommended by the SRC. Treatment will continue until PD or toxicity requiring removal from study.

5.2.2. Pomalidomide

Pomalidomide (POMALYST[®]) will be provided to research patients for the duration of their participation in this study at no charge to them or their insurance providers. Pomalidomide will be provided in accordance with the Celgene Corporation's POMALYST REMST[™] or RevAid[®] program. Per the standard POMALYST REMST[™] and RevAid[®] program requirements, all physicians who prescribe pomalidomide for research patients enrolled into this study, and all research patients enrolled into this study, must be registered in and must comply with all requirements of the POMALYST REMST[™] and RevAid[®] program. Drug will be shipped to the patient's home or to the study site (in Canada only) for Investigational New Drug studies. Only enough pomalidomide for one cycle of therapy will be supplied to the patient each cycle. This is in accordance with the POMALYST REMST[™] and RevAid[®] programs.

Pomalidomide (POMALYST[®]) will be administered based on the current approved dose and schedule: 4 mg PO QD on Days 1 to 21 of a 28-day cycle (see Table 2). Pomalidomide

capsules should be swallowed whole, and should not be broken, chewed or opened. Patients should take pomalidomide at the same time each day, immediately following ACY-1215 dosing when applicable. Pomalidomide should be taken without food, at least 2 hours before or 2 hours after a meal. If a dose of pomalidomide is missed, it should be taken as soon as possible on the same day. If it is missed for the entire day, it should not be made up, rather it should be taken at the next scheduled time point. Patients who take more than the prescribed dose of pomalidomide should be instructed to seek emergency medical care if needed and contact study staff immediately. Pomalidomide will be sent to the patients' home or to the study site (in Canada only) via the POMALYST REMSTTM and RevAid[®] programs (see Appendix 9.3 and Appendix 9.4, respectively).

5.2.3. Dexamethasone

All patients will receive dexamethasone, which will be taken PO QD on Days 1, 8, 15, and 22 of each 28-day cycle (see Table 2). For patients \leq 75 years of age, the starting dose of dexamethasone will be 40 mg; for patients who are $>$ 75 years of age, the starting dose of dexamethasone will be 20 mg.

5.2.4. Planned Study Drug Doses

The planned study drug doses for the combination regimen are shown in Table 2.

Table 2 **Planned Dose Escalation**

Phase 1b				
Dose Level ^a	N	ACY-1215	Pomalidomide	Dexamethasone ^b
-2	3-6	160 mg QD on Days 1-5, and 8-12	4 mg QD Days 1-21	40 mg QD Days 1, 8, 15, 22
-1	3-6	160 mg QD on Days 1-5, 8-12, and 15-19	4 mg QD Days 1-21	40 mg QD Days 1, 8, 15, 22
1	3-6	160 mg QD on Days 1-21	4 mg QD Days 1-21	40 mg QD Days 1, 8, 15, 22
2	3-6	240 mg QD on Days 1-21	4 mg QD Days 1-21	40 mg QD Days 1, 8, 15, 22
3	3-6	160 mg BID on Days 1-21	4 mg QD Days 1-21	40 mg QD Days 1, 8, 15, 22

Key: BID = twice daily, QD = once daily.

Note: treatment cycle is 28 days.

^a Patients will be initially enrolled at Dose Level 1. If 2 or more patients experience a DLT within the 28-day cycle, patients will subsequently be enrolled at Dose Level -1. If 2 or more patients experience a DLT at Dose Level -1 within the 28-day cycle, patients will subsequently be enrolled at Dose Level -2

^b Patients \leq 75 years of age will receive 40 mg of dexamethasone; patients $>$ 75 years of age will receive 20 mg.

Based on the interim evaluation of the safety and tolerability data of the previous dose level, it may be decided to investigate an intermediate dose level not specified in Table 2 (as applicable) (see Section 5.2.5). If this occurs, the IRBs/IECs will be informed of the intermediate dose level(s).

The SRC will review safety data after the first 3 patients have completed Cycle 1 and make the determination to initiate enrollment of another 3 patients into the next dose level. Based on these evaluations the SRC may decide that enrollment at an alternate starting dose or an intermediate dose level not specified in this protocol may take place. If this occurs, the

IRB/IEC will be informed immediately of the alternate starting dose or intermediate dose level(s).

5.2.5. Dose Escalation Procedure

Study drug doses will be escalated sequentially after the SRC reviews safety data from all patients enrolled in each dose cohort to confirm any DLTs that were experienced and make a determination regarding enrollment in the next dose cohort. Each of the first 3 patients in the dose cohort must have completed Cycle 1 (28-day cycle) to be eligible for SRC review and for a decision to be made regarding enrollment into the next dose level (see Section 4.8). Based on the interim evaluation of the safety and tolerability data of the previous dose level, it may also be decided that escalation will take place at an intermediate dose level not specified in Table 2 (as applicable). If this occurs, the IRBs/IECs will be informed of the intermediate dose level(s). The SRC may be convened earlier at the discretion of the Sponsor if important safety issues arise requiring the attention of the committee.

Determination of MTD: Dose escalation rules

Three patients are to be enrolled in each Dose-Level Group. After 3 patients have completed Cycle 1 (28-day cycle) and:

- If none of the 3 patients experiences a DLT within the first 28 day cycle, and pending SRC review as described above, then an additional 3 patients will be enrolled into the next higher dose level.
- If one of the 3 initial patients in a Dose-Level Group experiences a DLT within the first 28-day cycle, then an additional 3 patients will be enrolled into that Dose-Level Group.
- If 2 or more patients within the expanded dose cohort experience a DLT within the first 28-day cycle, then the MTD has been exceeded and no further dose escalations will occur.
- If no more than one of the 6 patients experiences a DLT within the first 28-day cycle, then the next dose cohort of 3 patients will be enrolled at the next higher dose level.

The MTD will be defined as the highest dose level at which no more than 1 of 6 patients experiences a DLT within the first 28-day cycle. If no more than 1 of these 6 patients experiences a DLT within the first 28-day cycle, then the last dose level enrolled to meet these criteria may be identified as the recommended dose for the Phase 2 segment of the study.

Teleconferences or email communication between the Sponsor or designee and the clinical study sites will occur weekly to monitor for DLTs and to communicate enrollment to the next dose level.

Patients who discontinue from the study for reasons other than DLT (e.g., non-compliance, patient request) before completing Cycle 1 will be replaced.

The use of hematopoietic growth factors will not be permitted during screening in the Phase 1 or Phase 2 segments of the study or in Cycle 1 of the Phase 1b segment of the study; however, they will be permitted in Cycle 2 and subsequent cycles. The use of bisphosphonates is permitted.

Patients may not be enrolled in more than 1 dose cohort. Patients enrolled into the Phase 1b segment of the study cannot be enrolled into the Phase 2 segment upon discontinuation from Phase 1b.

Complete blood counts will be monitored at least every 14 days during Cycle 2 and then at least at the first day of every cycle thereafter.

5.2.6. Dose-limiting Toxicity

Before each scheduled study drug dose administered in the clinic, the patient will be evaluated for possible toxicities that may have occurred after the previous dose(s). Toxicities are to be graded according to the NCI CTCAE, Version 4.0. If a toxicity is not classified in the CTCAE, then it should be classified according to the criteria presented in Section 6.1.8.4.

The Investigator is to assess the relationship of a toxicity to each study drug. If a toxicity is considered to be related to a particular drug(s), then the dose of the drug(s) to which the toxicity is considered related may be modified per the applicable algorithm in the following subsections. Conversely, if the toxicity is considered unrelated to a particular drug(s), then no modification of that drug(s) is required. For toxicities observed that may be attributable to pomalidomide (see Table 6) or dexamethasone (see Table 8), dose reductions should be attempted with these treatments prior to reducing the dose of ACY-1215.

The following AEs occurring during Cycle 1 that are considered to be ACY-1215-related will be considered to be DLTs:

Hematologic toxicity:

- Grade 4 neutropenia ($ANC < 500/\mu L$), lasting > 5 days, or
- Febrile neutropenia (fever $\geq 38.5^{\circ} C$ and $ANC < 1,000/\mu L$), or
- Grade 4 thrombocytopenia (platelet count $< 25,000/\mu L$), or

Grade 3 or 4 ACY-1215-related Non-hematologic toxicity:

- All other Grade 3 or Grade 4 non-hematologic toxicity with the exception of:
 - Grade 3 or 4 nausea, vomiting or diarrhea (Patients must have received optimal symptomatic treatment for Grade 3 or 4 nausea, vomiting, or diarrhea to be considered a DLT).
 - Grade 4 transaminitis (serum transaminase $> 20 \times$ upper limit of normal [ULN]) is a DLT, while Grade 3 transaminitis (serum transaminase $> 5 \times$ ULN) must be present for ≥ 7 days to be considered a DLT.
 - Other asymptomatic Grade 3 and 4 laboratory investigations, excluding cardiac function tests, may be evaluated by the SRC to determine whether dose cohorts should be expanded.
- Delay of the start of Cycle 2 by > 7 days due to ACY-1215-related AE.

Toxicity management procedures for ACY-1215 are presented in Table 4 and Table 5. No dose modifications for ACY-1215 are to be performed in Cycle 1.

5.2.7. Maximum Tolerated Dose

The DLT dose level is defined as the dose level of ACY-1215+pomalidomide+dexamethasone at which ≥ 2 of up to 6 patients experience a DLT. The MTD is defined as the dose level of ACY-1215+pomalidomide+dexamethasone immediately below the DLT dose level. Following the identification of the MTD, or recommended Phase 2 dose, up to 6 additional patients may be enrolled at this dose. When all 6 patients have completed the 28-day cycle at the MTD, the

SRC will review all Phase 1b safety data to determine the recommended dose of ACY-1215 to be used in the Phase 2 segment of the study.

5.2.8. Dose Modifications

Before each scheduled study drug dose administered in the clinic, the patient will be evaluated for possible DLTs that may have occurred after the previous dose(s) as described in Section 5.2.6. If a toxicity is considered to be related to a particular drug(s), then the dose of the drug(s) to which the toxicity is considered related may be modified per the instructions outlined in Section 5.2.8.1, Section 5.2.8.2, and Section 5.2.8.3. Conversely, if the toxicity is considered unrelated to a particular drug(s), then no modification of that drug(s) is required.

No dose modifications for ACY-1215 are to be performed in Cycle 1. After Cycle 1, patients who are unable to tolerate ACY-1215 treatment may have the dose reduction steps presented below until a tolerable dose is achieved.

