Patients may not be enrolled in more than 1 dose cohort. Patients enrolled into the Phase 1b segment of the study cannot be enrolled into the Phase 2 segment upon discontinuation from Phase 1b.

Confirmation of the Safety of the MTD

Following the identification of the MTD or identification of the recommended Phase 2 dose, up to 6 additional patients may be enrolled at this dose. When all 6 patients have completed the 28-day cycle at the MTD, the SRC will review all Phase 1b safety data to determine the recommended dose of ACY-1215 to be used in the Phase 2 segment of the study. For all patients enrolled in the Phase 1b MTD segment, following the completion of Cycle 1, efficacy assessments will be conducted every cycle for the duration of the treatment period.

PHASE 2 SEGMENT

When the SRC has determined a recommended Phase 2 dose of ACY-1215, the Phase 2 segment will be initiated. Treatment will continue until PD or toxicity requiring removal from study.

Study Day 1 is defined as the first day the patient receives study drug.

Based on findings from the Phase 1 segment of the study and as recommended by the SRC, the ACY-1215 dose and schedule to be administered in the Phase 2 segment will be 160 mg PO QD on Days 1 to 21 of a 28-day cycle. Pomalidomide will be administered based on the current approved dose and schedule: 4 mg PO QD on Days 1 to 21 of a 28-day cycle. The starting dose of dexamethasone will be 40 mg QD on Days 1, 8, 15 and 22 of each 28-day cycle for patients who are \leq 75 years of age. For patients who are $>$ 75 years of age, the starting dose of dexamethasone is 20 mg QD on Days 1, 8, 15, and 22 of each 28-day cycle. CBC will be conducted every 7 days for Cycle 1, every 14 days for Cycle 2, and on Day 1 of each cycle beginning with Cycle 3.

The use of bisphosphonates is permitted. The use of hematopoietic growth factors will not be permitted during screening in the Phase 1 or Phase 2 segments of the study or in Cycle 1 of the Phase 1b segment of the study; however, they will be permitted in Cycle 2 and subsequent cycles.

Treatment with myeloid growth factors is encouraged when ANC $<$ 1,000/ μ L.

Dose Interruption and Modification:

Dose interruption and reduction for ACY-1215, pomalidomide, and dexamethasone due to DLTs can be found in Section 5.2.8.

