5.2.8.1. ACY-1215

Patients must remain on their assigned ACY-1215 dose in Cycle 1 during the dose escalation phase of the study, or be withdrawn from the study. If toxicity attributable to pomalidomide or dexamethasone is seen during Cycle 1, dose reductions may be made as described in Table 6 and Table 8. Patients should receive 80% of planned doses to be evaluable for SRC review.

For toxicities observed that may be attributable to pomalidomide (see Table 6) or dexamethasone (see Table 8), dose reductions should be attempted with these treatments prior to reducing the dose of ACY-1215.

After Cycle 1, patients who are unable to tolerate ACY-1215 treatment may have the dose reduction steps presented in Table 3 until a tolerable dose is achieved.

Table 3 ACY-1215 Dose Modifications

Dose level	Starting dose of ACY-1215	1 st dose reduction	2 nd dose reduction
-2	160 mg QD on Days 1-5, and 8-12	80 mg QD on Days 1-5, and 8-12	NA
-1	160 mg QD on Days 1-5, 8-12, and 15-19	80 mg QD on Days 1-5, 8-12, and 15-19	NA
1	160 mg QD on Days 1-21	80 mg QD on Days 1-21	NA
2	240 mg QD on Days 1-21	160 mg QD on Days 1-21	80 mg QD on Days 1-21
3	160 mg BID on Days 1-21	160 mg QD on Days 1-21	80 mg QD on Days 1-21

Table 4 Dose Modification Instructions for ACY-1215 for Hematologic Toxicities

Toxicity	Dose Modification
Neutropenia (1st occurrence): 
• ANC < 500/μL or febrile neutropenia (fever \geq 38.5°C and ANC < 1,000/μL)• ANC return to \geq 500/μL	Interrupt ACY-1215 treatment, follow CBC weekly. Resume ACY-1215 at one dose level lower than at the time of the first occurrence per Table 3. For the second occurrence of neutropenia (each subsequent drop of ANC < 500, interrupt and follow as above and resume at one dose level below the current dose.
Thrombocytopenia (1st occurrence): 
• Platelets < 25,000/μL• Platelets return to \geq 50,000/μL	Interrupt ACY-1215 treatment, follow CBC weekly. Resume ACY-1215 at one dose level lower than at the time of the first occurrence per Table 3. For the second occurrence of thrombocytopenia (each subsequent drop of platelets < 25,000), interrupt and follow as above. When platelet count returns to 50,000, resume at one dose level below the current dose.

Table 5: Dose Modification Instructions for ACY-1215 for Non-hematologic Toxicities

Toxicity	Dose Modification

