5.2.8.2. Pomalidomide

Toxicities considered related to pomalidomide are to be managed as shown in Table 6 and Table 7.

Table 6 Dose Modification Instructions for Pomalidomide for Hematologic Toxicities

Toxicity	Dose Modification
Neutropenia Grade 4 neutropenia (ANC < 500/ μ L) or Febrile neutropenia (fever \geq 38.5°C and ANC < 1,000/ μ L)	Hold the pomalidomide dose for remainder of cycle. If the patient was not receiving Granulocyte colony-stimulating factor (GCSF) therapy, initiate GCSF therapy at the discretion of the treating physician. On Day 1 of next cycle, continue GCSF as needed and maintain dose of pomalidomide if neutropenia was the only DLT (except during the first cycle for patients enrolled into the MTD segment of the study). Otherwise, decrease pomalidomide by one dose level at start of next cycle. (Note, ANC must be \geq 500/ μ L in the US and Canada and \geq 1,000/ μ L in the EU to restart dosing)
Grade 4 Thrombocytopenia (Platelets < 25,000/ μ L)	Hold the dose for remainder of cycle. Decrease pomalidomide by one dose level when dosing is resumed at next cycle. (Note, platelet count must recover to \geq 50,000/ μ L to restart dosing)

Table 7 Dose Modification Instructions for Pomalidomide for Non-hematologic Toxicities

Toxicity	Dose Modification
Rash = Grade 3	Hold pomalidomide dose for remainder of cycle. Decrease by one dose level when dosing restarted at next cycle (rash must resolve to \leq Grade 1).
Rash = Grade 4 or Blistering	Discontinue pomalidomide dose and discontinue patient from study.
Constipation \geq Grade 3	Hold pomalidomide dose for remainder of cycle. Initiate bowel regimen. Decrease pomalidomide by one dose level when dosing restarted at next cycle (constipation must resolve to \leq Grade 2).
VTE \geq Grade 3	Hold pomalidomide dose for remainder of cycle. Initiate anti-coagulation treatment. Maintain pomalidomide dose level when dosing restarted at next cycle at discretion of treating physician.
Hypo/hyperthyroidism \geq Grade 2	Hold dose for remainder of cycle. Initiate appropriate medical therapy. Maintain dose level when dosing restarted at next cycle at discretion of treating physician.
Peripheral Neuropathy = Grade 3	Hold pomalidomide dose for remainder of cycle. Decrease pomalidomide by one dose level when dosing restarted at next cycle (neuropathy must resolve to \leq Grade 1).
Peripheral Neuropathy = Grade 4	Discontinue pomalidomide and discontinue patient from study.

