7.3. Populations for Analysis

For both Phase 1 (MTD) and Phase 2 (Open-label Treatment):

- Safety Population – all patients who receive at least 1 dose of study medication.
- Intent-to-Treat (ITT) Population – all patients.
- Efficacy Evaluable (EE) Population – all patients who meet eligibility criteria, receive at least 14 doses of study drug (i.e., ACY-1215, pomalidomide and low-dose dexamethasone) at the MTD, and have at least one post-baseline efficacy assessment. Safety analyses will be performed on the Safety Population, defined as all patients who receive at least 1 dose of study medication.

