7.5. Analysis Schedule

7.5.1. Interim Analysis

The interim analysis with the first 30 evaluable patients will be conducted using a one-sided 95% CI estimate for the response rate. If the lower bound of the 95% CI estimate with the 30 patients is $\geq 29\%$, the SRC may recommend either terminating the study at the interim based on treatment superiority, or continuing the study as planned. If the lower bound is $< 29\%$, various predicted lower bounds of one-sided 95% CIs for the response rate will be constructed to further guide the SRC's recommendation. For example, assuming a true response rate of 44% for the remaining 36 patients, the expected lower bound of one-sided 95% CI with 66 evaluable patients will be calculated. If the expected lower bound is $\geq 29\%$, the SRC may recommend continuing the study as planned. If the expected lower bound with 66 evaluable patients is $< 29\%$, another simulation will be run with 86 evaluable patients. If the resulting lower bound is acceptable (e.g., close to or $\geq 29\%$), the SRC may recommend expanding the sample size by 20 patients. If the resulting lower bound is not acceptable (e.g., $< 29\%$), the SRC may recommend terminating the study for futility. In addition, the expected lower bound of the one-sided 95% CI when the true response rate is equal to the observed value at the interim analysis will be calculated. The resulting scenario will be similar to the previous one: if the expected lower bound is $\geq 29\%$, the SRC may recommend continuing the study as planned, if the lower bound is $< 29\%$, the SRC may recommend expanding the sample size by 20 patients. Additional simulations with other possible response rates (for example, assuming a 40% response rate), with or without adaptation, will also be conducted; the SRC will review all simulation results to make a recommendation at the interim. Furthermore, with the potential

adaptations at the interim, we find via an extensive simulation study the final CI estimate would have the accurate coverage level. Therefore, no statistical penalty or adjustment will be needed for the final inferential statistical procedure for the response rate.

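### Sections 5.2.6 and 5.2.8 bar ACY-1215 dose changes in Cycle 1 without limiting the bar to Phase 1b; read literally, this blocks the Table 4 and Table 5 holds in Phase 2

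*Combined protocol and SAP*

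**What the plan says.** Section 5.2.8 (Dose Modifications) states: "No dose modifications for ACY-1215 are to be performed in Cycle 1". It then opens the reduction steps once Cycle 1 is over. The same prohibition closes Section 5.2.6, directly after that section points to Tables 4 and 5 for toxicity management. Neither section names a phase.

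Section 5.2.8.1 begins more narrowly: "Patients must remain on their assigned ACY-1215 dose in Cycle 1 during the dose escalation phase of the study", with withdrawal from the study as the alternative. Later in the same section the limit is gone: "After Cycle 1, patients who are unable to tolerate ACY-1215 treatment may have the dose reduction steps presented in Table 3".

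Table 4 covers ANC below 500/µL, febrile neutropenia and platelets below 25,000/µL. Its instruction is "Interrupt ACY-1215 treatment, follow CBC weekly. Resume ACY-1215 at one dose level lower than at the time of the first occurrence". Table 5 requires a hold for Grade 3 non-hematologic toxicity and a restart one level lower. Neither table is limited by cycle or phase.

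The Phase 2 segment of the synopsis gives no separate rule. It says: "Dose interruption and reduction for ACY-1215, pomalidomide, and dexamethasone due to DLTs can be found in Section 5.2.8".

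**The concern.** A Phase 2 site with an ACY-1215-related Table 4 or Table 5 event in Cycle 1 follows the synopsis to Section 5.2.8 and meets two instructions that cannot both be carried out. One says no dose modification in Cycle 1. The other, under a table titled as dose modification instructions, says to stop the drug and restart lower.

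In Phase 1b a Cycle 1 ban has a purpose, because it keeps the DLT assessment tied to the assigned dose. In Phase 2 the documents give it none. What is at stake is whether a patient with a severe drug-related cytopenia, or a Grade 3 non-hematologic toxicity, is taken off ACY-1215 promptly in the first cycle.

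**Working it through.** No figure in the plan bears on this point, so the check is a comparison of the texts followed by a dose count.

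**Texts side by side**

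| Place | Rule for ACY-1215 | Cycle limit | Phase limit |
|---|---|---|---|
| Synopsis, Phase 1b segment | No modification; reductions afterwards | Cycle 1 | Phase 1b, by placement |
| 5.2.6 | No modification | Cycle 1 | None stated |
| 5.2.8 | No modification; reductions afterwards | Cycle 1 | None stated |
| 5.2.8.1, opening | Stay on assigned dose or be withdrawn | Cycle 1 | Dose escalation phase |
| 5.2.8.1, lead-in to Table 3 | Reductions allowed | After Cycle 1 | None stated |
| Table 4 | Interrupt, resume one level lower | None | None |
| Table 5 | Hold, restart one level lower | None | None |
| Synopsis, Phase 2 segment | Go to 5.2.8 for interruption and reduction due to DLTs | DLTs are Cycle 1 events (5.2.6) | Phase 2 |

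The last row sends Phase 2 Cycle 1 events to a section whose own sentence forbids acting on them. Elsewhere the plan does limit a Cycle 1 exception by phase. Table 6, for pomalidomide, words its exception as "except during the first cycle for patients enrolled into the MTD segment of the study". Sections 5.2.6 and 5.2.8 have no such phrase.

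**Dose count, one patient, platelets below 25,000/µL**

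Inputs: 160 mg once daily on Days 1 to 21 (Section 5.2.1); blood counts every 7 days in Cycle 1, with results reviewed before dosing (Section 6.1.7.1); first reduction to 80 mg (Table 3); platelets back to at least 50,000/µL before resuming, with weekly counts (Table 4).

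Planned Cycle 1 total: 21 × 160 = 3,360 mg.

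Event on the Day 8 count:
- Ban applied, covering interruption: 21 − 8 + 1 = 14 doses left; 14 × 160 = 2,240 mg.
- Table 4 applied: hold from Day 8. If recovery is seen on Day 15, 7 × 80 = 560 mg; if not, 0 mg.
- Difference: 2,240 − 560 = 1,680 mg up to 2,240 − 0 = 2,240 mg, or 50% to 67% of 3,360 mg.

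Event on the Day 15 count:
- Ban applied: 21 − 15 + 1 = 7 doses; 7 × 160 = 1,120 mg.
- Table 4 applied: the next weekly count is Day 22, after the last dosing day, so 0 mg.
- Difference: 1,120 mg, or 33% of 3,360 mg.

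**If the ban covers reduction but not interruption**

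The Day 8 patient is held under either reading. With recovery on Day 15, the comparison is 7 × 160 = 1,120 mg against 560 mg, a difference of 560 mg (17% of 3,360 mg). Without recovery by Day 15, and for a Day 15 event, there is no difference within Cycle 1.

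**The case against.** The best answer is that the intent is plain. The synopsis prints the identical prohibition inside its Phase 1b segment, between the DLT definition and the escalation rules. Its Phase 2 segment leaves it out and refers to interruption and reduction for DLTs, which presupposes action in Cycle 1. Section 5.2.8.1 ties the duty to stay on dose to the escalation phase. This stands as to intent, and a reader who infers that the sponsor meant to ban Phase 2 Cycle 1 holds would be going beyond the documents. It does not repair the body text. Sections 5.2.6 and 5.2.8 are unscoped, and Section 5.2.8.1 itself returns to an unscoped sentence about reductions.

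Second, the larger dose figures assume that interruption counts as a modification. Usage is mixed. The synopsis names interruption and modification separately and Table 3 lists reductions only, but Table 4 puts interruption under dose modification. The assumption is arguable, so both cases are shown above.

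Third, other rules narrow the problem. ACY-1215 changes apply to toxicity judged related to it; toxicity attributable to pomalidomide or dexamethasone is to be handled by reducing those drugs first; Table 6 holds pomalidomide for Grade 4 neutropenia, febrile neutropenia or platelets below 25,000/µL when these are considered related to it; and Section 4.6 allows withdrawal for an unacceptable adverse event. These points reduce how often the conflict arises. They do not say what to do with ACY-1215 when the event is attributed to it.

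A reader might also infer that Phase 2 lacks toxicity oversight, since Section 7.5.1 deals with response rate and says "the SRC will review all simulation results to make a recommendation at the interim". The documents do not support that. Section 4.8 gives the SRC a safety remit during the study, using data defined in a charter that is not among the documents. Section 7.1 lets it weigh all the interim information, and Section 3.5 allows termination for unacceptable risk.

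**Conclusion.** The conflict in the body text is real and small in extent: a missing scope phrase in a safety instruction. For an ACY-1215-related platelet count below 25,000/µL on Day 8 of Phase 2 Cycle 1, the literal ban means up to 14 further doses at 160 mg. That rests on the ban covering interruption and on the site following it over Table 4. If the ban covers reduction only, the difference is at most 560 mg. The documents give no frequency for such events, so no patient count is offered, and nothing here suggests that 160 mg daily is too toxic.

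A reader might infer that the choice of reading also settles who enters the primary efficacy set, because Section 7.3 asks that patients "receive at least 14 doses of study drug (i.e., ACY-1215, pomalidomide and low-dose dexamethasone) at the MTD". Section 7.6.7, which specifies the primary analysis, omits the clause about the MTD, so a patient held on Day 8 and resumed at 80 mg can still qualify on reaching 14 doses. The difference between those two definitions is a separate matter.

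**What to change.** - In Sections 5.2.6 and 5.2.8, end the prohibition with: *in Cycle 1 of the Phase 1b segment*. Both places need the edit, or the contradiction remains.
- In Sections 5.2.8 and 5.2.8.1, limit to Phase 1b the sentences that open reductions only once Cycle 1 is over.
- Add to Section 5.2.8: *In the Phase 2 segment, Tables 3 to 5 apply from Cycle 1.*

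The cost is a few words in three sections. Sample size, error rate, visits and data collection do not change. The downside is slightly lower Cycle 1 exposure to ACY-1215 in the patients who are held or reduced, as Tables 4 and 5 already provide.
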